Cover Page for ClinicalTrials.gov

Official Title of the Study:

Sex-specific Adaptation to Different Resistance Exercise Programs in Older Adults

Date of the document:

April 22, 2019

Objectives

The objectives of this study are to identify the sex-specific effects of low-velocity, high-load resistance training (RT) versus high-velocity, low-load power training (PT) on skeletal muscle function at the whole muscle, cellular and molecular levels in older adults.

Design

We will test our hypothesis by having healthy, sedentary older (65-75 years old) men and women exercise one leg using RT and the contralateral leg using PT, and examining muscle function from the molecular, cellular and whole muscle levels. This within subject, unilateral training design provides a powerful model to evaluate training differences by reducing between-subject variability. Unilateral exercise, with one leg exercised and the other as a control, has been commonly used in older populations to examine muscle gene expression to myofibrillar ultrastructure to whole muscle performance.

Methods

Recruitment. Healthy older (65-75 years) men and women will be recruited from Amherst, MA and surrounding areas. Using the 2010 census data, ~45,000 volunteers between the ages of 65-75 live within 25 miles of Amherst. The best evidence of our recruitment capacity in this area is the track record of members of the investigative team for conducting recent research studies in older adults and requiring multiple biopsies.

Pre-exercise testing (Baseline). Baseline testing will occur prior to exercise and include assessments of body composition, physical activity, and whole skeletal muscle to cellular and molecular function.

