Body composition, physical activity and function: Body mass, total and regional body composition will be assessed by dual energy x-ray absorptiometry (DEXA) (2); knee extensor fat content (% total) and fat-free muscle mass by magnetic resonance imaging (MRI); and 7 days of free-living physical activity by Actigraph GT3X-BT monitor. Physical activity will be matched across sex groups to reduce this confounding factor, per our studies in diseased and healthy older adults. Participants will also complete the Advanced Short Performance Physical Battery (SPPB-A) to assess mobility function. The SPPB-A includes timed measures of walking, static and dynamic balance assessments (including single leg), and repeated chair stands. As one leg is undergoing RT and the other PT, single leg balance assessments will be performed for each leg to examine differences in RT and PT, as it has been shown to increase with RT. A single-step test (SST), which correlates well with other lower limb functional performance measures, will also be performed on each leg. To perform the SST, volunteers stand on one leg (test leg) on a 15 cm high, single step and must touch the ground with their contralateral leg by performing a squat with the test leg and return to the standing position. The time required to repeat this movement 20 times is recorded. The non-test leg is held straight by a knee immobilizer brace.

Whole skeletal muscle function: Knee extensor (KE) peak torques for each leg will be measured on an isokinetic dynamometer (Biodex System 4) during maximal voluntary contractions at 0, 60, 120, 180, 240, 300 and 500°s⁻¹. Range of motion will be 70°, beginning at 80° of flexion, with 2 repetitions per velocity. Maximal contractile velocity will be obtained from the 500°s⁻¹ trial. Coin toss will determine which leg is tested first, and the order of contraction velocity will begin and end with 120°s⁻¹, to evaluate whether fatigue occurred, with the remainder of the contractions performed in random order. Motor point stimulation will be applied to the resting muscle to determine maximal rates of torque development (RFD_{stim}) and relaxation (RFR_{stim}) at 0°s⁻¹. In addition to quantifying intrinsic whole-muscle contractile properties, these values will be compared with the rates during ballistic, maximal voluntary contractions (RFD_{vol},

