Resistance exercise training. Our overall approach to RT and PT training is based on studies, as well as our preliminary work, that have demonstrated improvements in whole muscle and single fiber function are apparent within 16 wks or less. After recovery from the baseline biopsy (~1 wk), volunteers will begin a 16 wk, facility-based, resistance exercise training program (3 times/wk). Volunteers will have their dominant or non-dominant leg randomly assigned to RT with the contralateral leg assigned to PT (1:1 allocation). The training program will include: 1) leg press; 2) knee extension; and 3) knee flexion. Each exercise will be performed for RT for one leg and then for PT in the other leg before moving on to the next exercise. Prior to and at the end of each exercise session, volunteers will warm-up/cool-down on an exercise bike (~30-50 W) for 5 min. Based upon the National Strength and Conditioning Association guidelines and our resistance training of older adults, we expect the exercise session during to be less than one hour. Patients will be required to complete at least 90% or greater of the prescribed sets and 80% of the training sessions over the 16 wk period to be included in the analyses.

Low-velocity, high-load resistance training (RT): The intensity of the RT program will be 80% of one repetition maximum (1RM) for 3 sets of 8 repetitions, as recommended for maximum strength gains and as previously performed by our laboratories. Concentric and eccentric contraction phases for RT will last 2-3 sec. Exercise intensity for RT will progress over the first 3 weeks, as we have previously done. The first week will be 50% 1RM for 1 set of 10 repetitions, second week will be 60% 1RM for 2 sets of 8 repetitions and the third week will be 70% 1RM for 3 sets of eight repetitions. 1RM will be updated bi-weekly.

High-velocity, low-load power training (PT): The intensity of the PT program will be 40% 1RM for 3 sets of 16 repetitions. The PT program will be performed at 40% 1RM, instead of the 80% 1RM in the RT program, in order to increase the contractile speed during training and maximize the potential to improve whole muscle performance. The ability of 40% 1RM to better ameliorate age-related decreases in whole muscle performance is based upon the findings that power

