Cover Page for ClinicalTrials.gov

Official Title of the Study:

Sex-specific Adaptation to Different Resistance Exercise Programs in Older Adults

Date of the document:

April 22, 2019

Our goal is to assess the main effects of training (traditional low-velocity, high-load resistance training and high-velocity, low-load power training versus baseline) and sex and determine if training alters muscle function differently in men and women (training by sex interaction). Primary outcomes include: (1) whole muscle: peak isometric torque and isokinetic power; (2) cellular: single fiber specific force, velocity, power; (3) molecular: myofilament stiffness (A-elastic), myosin rate of force production, myosin attachment time (t_{on}). We will model the data from this project with linear mixed models. This class of models is appropriate since it models the intra-participant correlation that is anticipated to result from the repeated measurements on each person, both multiple fibers and training protocols. This model and associated testing procedures such as likelihood ratio tests and large sample confidence intervals for coefficient contrasts will allow us to assess the main effects (treatment effects and sex effects) and their interactions. It also can accommodate other covariates, such as muscle size, if necessary. The analyses will be done in R and will use the lme4 library for linear mixed models. Transformations to normality, adjustments for multiple testing, and assessments of the linear assumptions will be done as appropriate. Additionally, we will examine correlations among functional parameters at different anatomic levels to determine whether cellular and molecular phenotypes relate to whole muscle parameters.

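### No small-sample reference is named for the mixed-model tests; Kenward-Roger or Satterthwaite tests on the planned lme4 fit are a cheap improvement, whose value depends on the unstated n and, for fibre outcomes, on between-participant variation in training effects

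*SAP*

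**What the plan says.** The SAP is one paragraph. Its interaction aim is to "determine if training alters muscle function differently in men and women (training by sex interaction", which matches the protocol's Objectives: to "identify the sex-specific effects of low-velocity, high-load resistance training (RT) versus high-velocity, low-load power training (PT". On software it says: "The analyses will be done in R and will use the lme4 library for linear mixed models". For inference it names "associated testing procedures such as likelihood ratio tests and large sample confidence intervals for coefficient contrasts". A later sentence adds: "Transformations to normality, adjustments for multiple testing, and assessments of the linear assumptions will be done as appropriate". That list does not mention degrees of freedom or a t or F reference.

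The model is meant to handle correlation from "the repeated measurements on each person, both multiple fibers and training protocols", but the random-effects terms are not written out, nor is the choice between ML and REML.

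Neither document gives a sample size, an alpha level or a power statement. The protocol (Resistance exercise training) limits the analysis to people who complete 90% of the prescribed sets and "80% of the training sessions over the 16 wk period to be included in the analyses", so the analysed number may be smaller than the number enrolled.

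**The concern.** Sex varies only between participants. When training effects differ from person to person, the replicates for training-by-sex are participants, however many fibres are measured. Likelihood ratio tests referred to chi-square, and intervals built on 1.96, ignore the uncertainty in the estimated variances. With few participants, and with that variation present, such tests reject a true null too often and the intervals are too narrow. Training-by-sex is the central question of the trial, so this is where calibration matters most. A standard remedy exists for the very fit that the SAP plans.

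**Working it through.** **Inputs.** From the documents: the named tests; three training conditions (baseline, RT, PT), hence two degrees of freedom for training-by-sex; two whole-muscle primary outcomes and six fibre-level ones (three cellular, three molecular); for whole-muscle outcomes, "peak torques for each leg will be measured on an isokinetic dynamometer". Assumed, because the documents do not say: two-sided alpha of 5%, equal numbers of men and women, balanced data, and n (total analysed) from 12 to 100. The plan has no figure of its own to reproduce.

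**1. Training-by-sex likelihood ratio test, one value per condition or per leg and time.** The chi-square cut-off is c = 5.9915. True size under three random-effects structures:

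- (a) fully participant-specific training effects: P(F(2, n−3) > ((n−3)/2)(exp(c/n) − 1))
- (b) random intercept, one value per condition: P(F(2, 2n−4) > (n−2)(exp(c/(2n)) − 1))
- (c) random intercept, four leg-by-time values: P(F(2, 3n−4) > ((3n−4)/2)(exp(c/(3n)) − 1))

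At n=20 the thresholds are 8.5 × 0.3493 = 2.97, 18 × 0.1616 = 2.91 and 28 × 0.1050 = 2.94.

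| n | (a) | (b) | (c) |
|---|---|---|---|
| 12 | 10.6% | 8.2% | 7.0% |
| 20 | 7.8% | 6.7% | 6.1% |
| 40 | 6.3% | 5.8% | 5.5% |
| 100 | 5.5% | 5.3% | 5.2% |

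**2. Large-sample 95% interval for the RT-versus-PT-by-sex contrast.** Non-coverage is 2P(t(df) > 1.96) with df = n−2, 2n−4 or 3n−4: 5.9% to 7.8% at n=12, 5.5% to 6.6% at n=20, 5.2% to 5.7% at n=40. A t-based interval is wider by the ratio t(0.975, df)/1.96: 4% to 14%, 2% to 7% and 1% to 3% respectively.

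**3. Sex effect averaged over conditions.** Likelihood ratio size is P(|t(n−2)| > sqrt((n−2)(exp(3.8415/n) − 1))): 8.1%, 6.7%, 5.8% and 5.3% at n = 12, 20, 40 and 100. A baseline-referenced sex coefficient under a random intercept has more degrees of freedom. At n=20 its normal-reference Wald test has size 5.6% to 6.2% for assumed intraclass correlations of 0.3 to 0.8.

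**4. Fibre outcomes.** Simulation with 200,000 runs, n=20, three conditions, 10 fibres per condition, and participant variance assumed to be 20% of the total. The model has participant and participant-by-training effects, with variances constrained to be non-negative. The F test is a REML F on (2, 2n−4) degrees of freedom, a balanced-case approximation to Kenward-Roger.

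| Participant-by-training share of total variance | Likelihood ratio test | F test |
|---|---|---|
| 0 | about 4.3% | 3.2% |
| 1% | about 5.2% | 3.9% |
| 2% | about 5.7% | 4.3% |
| 5% | 6.6% to 6.7% | 4.9% |

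More fibres do not remove the excess: at a 5% share the likelihood ratio size is 6.1%, 6.6% and 6.8% with 5, 10 and 20 fibres.

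**5. Separate check: participant-by-training effect left out.** Take n=20, 10 fibres, 20% participant share and 5% participant-by-training share. The residual variance is 0.75. The training-by-sex mean square has expectation 0.75 + 10 × 0.05 = 1.25. The pooled residual is (540 × 0.75 + 36 × 1.25)/576 = 0.78, so F is inflated by 1.25/0.78 = 1.60. Its nominal cut-off is about 3.01, and the size is roughly exp(−3.01/1.60) = 15%. At a 10% share the same steps give a ratio of 1.7/0.7625 = 2.23 and a size of about 26%. With no participant variance in the total, the sizes are about 13% and 22%. These come from the random-effects structure. Changing the reference distribution would not cure them.

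**The case against.** The strongest reply is that the SAP excludes nothing. It introduces its methods as examples, and Kenward-Roger or Satterthwaite tests are compatible with it. Nothing in the documents shows that n is small, and at n=40 the excess is at most about 1.3 percentage points. This stands, and it limits the point to an improvement rather than an error.

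The direction is also not uniform. For six of the eight primary outcomes the likelihood ratio test is slightly conservative if participant-by-training variance is zero. At shares of 0 to 1% it is about as close to 5% as the corrected F test or closer; the F test is better calibrated from about 5%. This stands too. The benefit depends on that variance share as well as on n.

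The largest whole-muscle figures (10.6% and 7.8%) come only from structure (a). With a single value per condition, participant-specific training effects cannot be separated from residual error, so those figures are upper ends.

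A reader might infer that the trial's sex-by-training tests have inflated error. The documents do not support that without n. A reader might also infer from step 5 that fibres will be treated as replicates, with error rates of 15% or 26%. The SAP's reference to correlation from both fibres and training protocols may already intend the second level, so that inference is not supported either.

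What remains is that no small-sample method is named, and the SAP's list of steps to be taken as needed does not cover one.

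**Conclusion.** The point holds as a low-severity, inexpensive improvement. At an assumed 5% level with balanced data, the excess for training-by-sex on whole-muscle outcomes is about 2 to 5.6 percentage points at n=12, 1 to 3 at n=20, 0.5 to 1.3 at n=40 and at most 0.5 at n=100. For fibre outcomes it arises only if training effects vary between participants. At n=20 it is then up to about 1.7 points at a 5% share, against a deficit of about 0.7 points at a share of zero. All of this is conditional on n, alpha and variance shares that the documents do not give. If the planned n is 40 or more, the matter is minor. The random-effects specification for fibre outcomes is a separate question, with larger potential consequences if the participant-by-training level were omitted, and the documents do not show that it is.

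**What to change.** Add a few sentences to the SAP:

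- Fit the models by REML, and test fixed effects and contrasts with Kenward-Roger or Satterthwaite degrees of freedom and t-based intervals, using lmerTest or pbkrtest on the lme4 fit. Name a parametric bootstrap as the fallback if the fibre data are too unbalanced.
- For fibre outcomes, state a participant-by-training random effect alongside the participant effect.
- State the planned n and the alpha level, and report the analysed n afterwards.

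No new data or design change is needed. The price is the wider intervals shown in step 2 and a somewhat conservative test (about 3% to 4% at n=20) when the participant-by-training variance is near zero. That variance may also be estimated at or near zero in a small sample, and the SAP should say that the term is kept in that case.
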